3.1.3 Visit windows

For the Peak Pruritus NRS, weekly summary scores will be calculated using the 7 daily scores for each week, starting with randomization day (e.g. Days 1 to 7 for Week 1, Days 8 to 14 for Week 2), regardless of visit attendance days.

For Peak Pruritus NRS Week 16 score, the 7 days prior to the scheduled Week 16 timepoint (ie Days 106 to 112) will be used for calculation. However, only days prior to the first dose of IP in the extension period will be used for the Week 16 score derivation. If the Week 16 visit, and therefore the start of extension period IP dosing, occurs ahead of schedule (ie at Day 112 or earlier), then the 7 days prior to this day of first dose of extension period IP will be used for the Week 16 score, and the Week 15 score will be set to missing. If the Week 16 score cannot be calculated on the 7 daily scores, then an additional 1-day shift to assess the 8 daily scores before extension IP dose day will be assessed, and the Week 15 score will be set to missing. For Week 17 score, the scheduled 7 days before day 120 (ie Days 113-119) will be used. If the Week 16 visit occurs at Day 113 or later, Days 106 to 112 will be used in the Week 16 score as planned. Further details on scoring for daily Peak Pruritus NRS will be provided in Section 3.3.2.

For efficacy endpoints that present visit-based data, visit windows will be applied. The adjusted analysis-defined windows will be based on the collection schedule listed in the protocol and variables will be windowed to the closest scheduled visit for that variable.

Visit windows following baseline will be constructed in such a way that the upper limit of the interval falls halfway between two visits (the lower limit of the first post-baseline visit will be study day 2). If an even number of days exists between two consecutive visits, then the upper limit will be taken as the midpoint value minus 1 day. Visit windows are constructed so that every observation collected can be allocated to a particular visit. No visit windows will be defined for screening visits.

For assignment of data to adjusted analysis-defined visit windows, study day will be defined as follows:

$$(Date\ of\ assessment - date\ of\ randomization) + 1$$

Following this definition, for example if the day of randomization is study day 1 and date of assessment is the planned date of Visit 3 (Week 4), the study day will be 29 (28+1).

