3.3.2 Peak Pruritus Numeric Rating Scale

The proportion of participants with an improvement of ≥ 4 points in peak pruritus weekly score at Week 16 will be used as the second key secondary efficacy variable.

The Peak Pruritus NRS is a one-item daily assessment of the worst itch the participant experienced over the past 24 hours. This is recorded every evening from Visit 1 onwards on the electronic device supplied to the participants. The score ranges from 0 to 10, with 0 being “no itch” and 10 being “worst itch imaginable.” and so a reduction in score is considered an improvement.

If a participant has at least 4 non-missing daily scores in a 7-day week, the peak pruritus weekly score is defined as the sum of the available daily scores divided by the number of days with non-missing daily scores. If there are less than 4 non-missing daily scores, then the weekly score is missing for that week.

The second key secondary endpoint is a binary response that will classify a participant as a responder if there is an improvement of 4 or more points in peak pruritus weekly score at Week 16 relative to baseline. Otherwise, participants will be classified as a non-responder.

In the statistical analyses, a binary variable will take on value 1 if a participant is defined as a responder, and value 0 for non-responder, and will be used as the response variable for the efficacy analysis.

The change from baseline in peak pruritus score at Week 2 will be analyzed as a secondary endpoint.

Intercurrent events will be considered as described above in Section Intercurrent Events (Section 3.1.5). Participants with a missing baseline score will have missing change from baseline status. Intercurrent events will be considered for analyses and descriptive summaries.

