4.2.7.3 Change from baseline in EASI score

The secondary endpoint of change from baseline in EASI score will be analyzed by a MMRM model at Week 16.

The model will include change from baseline in EASI score as the dependent variable (derived for each participant and every scheduled visit up to Week 16); baseline EASI score as a continuous covariate; treatment, age at screening (≥ 12 to < 18 years/ ≥ 18 years), blood eosinophils at screening (< 300 cells/ μ L; ≥ 300 cells/ μ L), and visit as categorical factors; and treatment-by-visit as an interaction term. The strata variables will be used as recorded on the database. An unstructured variance-covariance matrix will be used to model within-subject errors, and the Kenward-Roger approximation will be used to estimate denominator degrees of freedom and to adjust standard errors, the OBSMARGINS option will be used to derive the LSMEAN estimates assuming mean values for the baseline covariates. If the model fails to converge, alternative variance-covariance models will be tried in the following order: Toeplitz, first-order regressive, compound symmetry.

For each visit, the model will be used to estimate the mean change from baseline for each treatment group (benralizumab 30mg Q4W and placebo) and difference between treatment groups, with corresponding 95% CIs and the p-value, corresponding to a 2-sided test.

The distributional assumptions of the MMRM model will be checked by examining plots of residuals. If the residuals suggest that it is unreasonable to assume that data follow a Normal distribution (eg, data are skewed and the constant variance assumption is not met), alternative models will be explored. For example, data may be log transformed prior to fitting the model, or a non-parametric method may be deemed more appropriate.

The observed means and mean changes from baseline will be summarized using descriptive statistics by treatment group and each scheduled visit up to Week 16.

Additional sensitivity analyses based on different missing data mechanism assumptions may be used to explore the robustness of any treatment effect, including

- Participants with rescue therapy use (from Day 29 onwards) will be imputed using LOCF approach and analyzed with analysis of covariance (ANCOVA);
- Treatment policy approach where all available data is included regardless of rescue use, and analyzed with MMRM;

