4.2.7.4 Change from baseline in peak pruritus numeric rating scale

The change from baseline in peak pruritus score will be analyzed using a MMRM model as described above for the change in EASI (Section 4.2.7.3). The change at Week 2 along with other supportive timepoints will be estimated from this model.

Descriptive summary statistics for scores and changes from baseline will be produced by treatment group and visit.

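### The MMRM fallback list holds only equal-variance covariance structures, so if the weekly itch model falls back, the Week 2 interval could be too wide and late-week intervals too narrow

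*SAP*

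**What the plan says.** SAP section 4.2.7.3 sets out the repeated-measures model for change in EASI. The starting point is sound: "An unstructured variance-covariance matrix will be used to model within-subject errors". On inference the same section states that "the Kenward-Roger approximation will be used to estimate denominator degrees of freedom and to adjust standard errors". If that model does not converge, "alternative variance-covariance models will be tried in the following order: Toeplitz, first-order regressive, compound symmetry". No heterogeneous version is named and no empirical standard error is planned. The response is "derived for each participant and every scheduled visit up to Week 16".

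Section 4.2.7.4 carries the model over to itch: change in peak pruritus "will be analyzed using a MMRM model as described above for the change in EASI". It adds: "The change at Week 2 along with other supportive timepoints will be estimated from this model". Section 3.3.2 gives the Week 2 result its status: "The change from baseline in peak pruritus score at Week 2 will be analyzed as a secondary endpoint". Under section 3.1.3 the itch score is weekly: "weekly summary scores will be calculated using the 7 daily scores for each week". The SAP does not say which weeks enter the itch model.

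Section 4.1 sets data after rescue use from Day 29, or after withdrawal, to missing for these models, so later weeks hold fewer observations.

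**The concern.** Toeplitz, first-order autoregressive (the listed "first-order" term is read that way here) and compound symmetry differ in how they model correlation between visits. In standard form all three share one variance across visits. An MMRM standard error at a given week is model-based, so when the variance truly differs by week the pooled value passes directly into that week's confidence interval and p-value. Kenward-Roger corrects for estimating the covariance parameters in small samples. It takes the form of the covariance as given.

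The exposure is greatest for itch. Its model may hold many more time points than the visit-based scales, and its named endpoint sits at Week 2, near one end of the series, where the variance of a change score is commonly smallest because the score is still strongly correlated with baseline. A pooled variance would then cost precision on the endpoint of interest and give false precision at the late supportive weeks.

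**Working it through.** The SAP states no figure for the covariance model and no SD by week, so there is no sponsor figure to reproduce. The check has three parts.

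**1. Parameter counts.** For t time points, unstructured needs t(t+1)/2 covariance parameters, Toeplitz t, and AR(1) or compound symmetry 2.
- t = 16 (all weekly scores to Week 16): 16 × 17 / 2 = 136, against 160 to 200 participants (SAP section 1.2). Toeplitz needs 16; AR(1) and compound symmetry need 2.
- t = 4 or 5 (illustrative for a visit-based scale): 10 or 15.

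**2. Effect of a common variance.** With complete data the treatment difference at week w has true SE = SD(w) × √(2/n) with n per arm. The pooled model uses the average variance over weeks, so

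ratio(w) = model SE / true SE = √(mean of SD² over the 16 weeks) / SD(w).

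Assumed inputs: SD of change rising from 1.2–1.8 at Week 1 to 2.5–2.6 at Week 16. Two shapes are used: a straight line, and a rise that levels off (exponential, time constant 5 weeks, scaled to reach the stated Week 16 value).

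| SD, Week 1 to 16 | Shape | Root mean square SD | SD Week 2 | Ratio Week 2 | Ratio Week 16 |
|---|---|---|---|---|---|
| 1.2 to 2.6 | linear | 1.948 | 1.293 | 1.51 | 0.75 |
| 1.2 to 2.6 | levelling | 2.225 | 1.467 | 1.52 | 0.86 |
| 1.5 to 2.5 | linear | 2.023 | 1.567 | 1.29 | 0.81 |
| 1.5 to 2.5 | levelling | 2.224 | 1.691 | 1.32 | 0.89 |
| 1.8 to 2.5 | linear | 2.161 | 1.847 | 1.17 | 0.86 |
| 1.8 to 2.5 | levelling | 2.302 | 1.934 | 1.19 | 0.92 |
| flat | – | – | – | 1.00 | 1.00 |
| 2.6 to 2.0 | linear | 2.307 | 2.560 | 0.90 | 1.15 |

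Example, first row: 1.948 / 1.293 = 1.51 and 1.948 / 2.6 = 0.75. Over the six rising rows the Week 2 SE is overstated by 17–52% and the Week 16 SE understated by 8–25%. The last two rows show that the effect vanishes for a flat SD and reverses for a falling one.

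**3. Simulation.** The linear 1.2 to 2.6 case was simulated with 80 per arm, 16 weeks and REML fits (300 replicates for compound symmetry and AR(1), 60 for Toeplitz). The true SEs are 1.293 × √(2/80) = 0.204 at Week 2 and 2.6 × √(2/80) = 0.411 at Week 16. With complete data all three fallbacks gave a mean model SE of 0.307 to 0.315 at both weeks. Coverage of the nominal 95% interval was 99–100% at Week 2 and 86–90% at Week 16. With about 31% lost by Week 16, coverage was 98–100% and 80–84%.

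**Does the unstructured fit fail?** In six simulated 16-week datasets of 160 participants, with 21–68% retained at Week 16, an EM fit reached a positive-definite unstructured solution every time. It grew less stable with more loss (condition number from about 600 to about 2,400). EM is not the REML fit that the SAP would run in SAS, and six datasets are few, so this neither shows failure to be likely nor rules it out.

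**The case against.** The strongest reply is that the primary specification is unstructured, which is unaffected, and that the list matters only after non-convergence. That stands: the point is conditional. A reader might infer from 136 parameters and 160 to 200 participants that fallback is likely. The documents do not support this. They do not fix the number of weeks in the itch model, and the probe fits all reached a solution. Plausible is as far as it goes.

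A reader might also extend the count to 52 weeks, which would give 1,378 parameters. Section 4.2.7.4 specifies no Week 52 model for itch change, and the Week 52 itch analysis in section 4.2.7.2 is a logistic responder analysis.

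The too-narrow Week 16 interval might be read as inflating the trial's type I error. It does not. Itch change at Week 16 is only a supportive timepoint. The key secondary itch endpoint at Week 16 is binary and analysed by logistic regression. No MMRM result is in the hierarchy of section 4.1.1, and the p-values concerned are nominal. The named Week 16 MMRM endpoints are collected at visits, where far fewer parameters are needed.

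Finally, section 4.2.7.3 does call for residual checks, mentions non-constant variance and allows alternative models to be explored. This is partial cover. The check is framed around non-normality, and the remedies offered as examples are a log transformation or a non-parametric method, not a heterogeneous covariance.

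**Conclusion.** The gap is real but conditional. All three listed fallbacks impose one variance on all visits, and nothing else in the SAP reliably corrects that. It bites only if two things happen: the unstructured itch model fails, and the SD of change varies by week. With an SD rising as assumed above, the Week 2 itch interval would be about 17–52% too wide and the Week 16 interval about 8–25% too narrow. The range depends on SDs and shapes that the SAP does not give, and the direction holds only if the SD rises. What is at stake is the precision reported for one named secondary endpoint and for supportive late weeks. The primary and key secondary tests and their error control are untouched. The change is worth making because it is cheap and removes a choice that would otherwise be made after the model has failed.

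**What to change.** Reword the fallback sentence in section 4.2.7.3 so that the order is heterogeneous Toeplitz, heterogeneous AR(1), heterogeneous compound symmetry, and only then the three homogeneous forms. Keep Kenward-Roger throughout. Replacing it with sandwich errors, or restricting itch to an early-weeks model, is debatable and not needed for this point.

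The cost is wording plus 15 extra variance parameters at 16 weeks: Toeplitz goes from 16 to 31, and AR(1) or compound symmetry from 2 to 17, against 136 for unstructured. Each week then has its own variance, so with complete data the standard error ratio returns to about 1.00 at Week 2 and Week 16. A heterogeneous structure may itself fail to converge, which is why the homogeneous forms stay at the end of the list.

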4.2.7.4 Change from baseline in peak pruritus numeric rating scale

The change from baseline in peak pruritus score will be analyzed using a MMRM model as described above for the change in EASI (Section 4.2.7.3). The change at Week 2 along with other supportive timepoints will be estimated from this model.

Descriptive summary statistics for scores and changes from baseline will be produced by treatment group and visit.

4.2.7.5 Change from baseline in POEM score

The change from baseline in POEM score at Week 16 and at Week 52 will be analyzed using MMRM model as described for the change in EASI (Section 4.2.7.3).

Descriptive summary statistics for scores and changes from baseline will be produced by treatment group and visit.

4.2.7.6 Change from baseline in SCORAD Index

The change from baseline in SCORAD Index at Week 16 and at Week 52 will be analyzed using MMRM model as described for the change in EASI (Section 4.2.7.3).

Descriptive summary statistics for scores and changes from baseline will be produced by treatment group and visit.

4.2.7.7 Change from baseline in DLQI

The change from baseline in DLQI at Week 16 and at Week 52 will be analyzed using MMRM model as described for the change in EASI (Section 4.2.7.3).

Descriptive summary statistics for scores and changes from baseline will be produced by treatment group and visit.

4.2.7.8 Change from baseline in CDLQI

The change from baseline in CDLQI at Week 16 and at Week 52 will be analyzed using MMRM model as described for the change in EASI (Section 4.2.7.3).

Descriptive summary statistics for scores and changes from baseline will be produced by treatment group and visit.

4.2.7.9 Serum benralizumab concentration

Serum benralizumab concentration will be summarized using descriptive statistics at each visit by treatment group based on the PK analysis set.

Serum benralizumab concentrations will be presented for both, the 16-week placebo-controlled treatment period and the Week 52 end of study reporting.

4.2.7.10 Immunogenicity

Anti-drug antibodies to benralizumab will be summarized using descriptive statistics at each visit by treatment group based on the safety analysis set. The ADA titres-time profiles of benralizumab by treatment group will be generated. The impact of ADA on PK and eosinophil level will be assessed. The potential association of ADA with safety and efficacy will be evaluated.

Further details are provided in Appendix 8.2.

ADA will be presented for both, the 16-week placebo-controlled treatment period and the Week 52 end of study reporting.

4.2.7.11 Proportion with an IGA response at Week 52

The proportion of participants with an IGA 0/1 and a decrease in IGA of ≥ 2 points at Week 52 relative to baseline, will be analyzed using a logistic regression model in a similar way to that described for the primary endpoint analyses (Section 4.2.6.1) comparing effects on the Q4W and Q8W maintenance regimens.

4.2.8 Safety Analyses

Safety analyses will be performed using the safety analysis set. Summaries will be presented by the 3 randomized treatment sequences (benralizumab 30 mg Q4W, benralizumab 30 mg Q8W and placebo/benralizumab) and the initial benralizumab 30 mg Q4W Total dose group, as noted in Sections 1.1.1 and 4.1.

A small number of key safety tables will also be presented for data in the extension period alone to explore the safety profile were a direct comparison of Q4W versus Q8W dosing can be made for participants previously receiving benralizumab, and to summarize time on benralizumab alone for participants previously receiving placebo.

Adverse event tables will be reported separately for the 16-week placebo-controlled treatment period and for the 36-week extension period. Some key adverse event tables will be repeated overall for Week 52 whole study.

Participants will be analyzed according to the treatment they received. In general, the baseline value for statistical analysis is the last non-missing value prior to administration of the first dose of IP. Safety data will be presented using descriptive statistics. No safety data will be imputed.

4.2.8.1 Adverse Events

TEAEs will be summarized separately for the on-treatment, on-study, and post-treatment periods, as defined in Section 3.4.1. The primary period of interest for safety summaries will be the on-treatment period for the 16-week placebo-controlled treatment period, and this is the only period that will be used for the placebo controlled first 16 weeks summaries. Summaries will also be produced for the on-treatment period of the extension period. Limited summaries will be produced for the on-study and post-treatment periods for the Week 52 end of study reporting summaries only. AEs in the pre-treatment period (with start date prior to the first dose of IP) will be listed only.

All summaries will be presented by treatment group and key tables will include exposure-adjusted rates to account for any differences in follow up.

The rate of TEAEs per person-years at risk will be calculated as (number of participants reporting the TEAE) / (total time with participants at risk of TEAE) for on-treatment and on-study periods. The post-treatment AEs will be listed. The total period at risk for each participant will be the duration of the on-treatment, post-treatment and on-study periods as defined in Section 3.4.1. Rates will be expressed in terms of events per 100 participant-years.

An overall summary table will be produced showing the number, percentage, and exposure-adjusted rate of participants with at least one TEAE in any of the following categories; TEAEs, SAEs, AEs with outcome of death, and AEs leading to discontinuation of IP (DAEs). AEs will be presented for each treatment group by system organ class (SOC) and preferred term (PT), including the number and percentage of participants reporting at least one event, number of events and exposure-adjusted rates, where appropriate.

TEAEs, AEs with outcome of death, SAEs and DAEs will be summarized by SOC and PT assigned to the event by MedDRA. For each PT, the number, percentage and exposure-adjusted rate of participants reporting at least one occurrence will be presented (ie, multiple occurrences of an AE for a participant will only be counted once).

A summary of the most common (frequency of >5%) TEAEs will be presented by PT. AEs and SAEs causing discontinuation of the IP and SAEs causing discontinuation from the study will be summarized by SOC and PT.

TEAEs, SAEs and DAEs will be summarized by PT and Investigator's causality assessment (related versus not related) and maximum intensity, including reporting of seriousness, death and events leading to discontinuation of IP, as well as other action taken related to IP. If a participant reports multiple occurrences of the same TEAE within the same study period, the maximum intensity will be taken as the highest recorded maximum intensity (the order being mild, moderate, and severe).

Other significant TEAEs will include but may not be limited to injection site reactions and hypersensitivity events. TEAEs of injection site reactions (high level term of injection site reactions) and hypersensitivity (standardized MedDRA query of hypersensitivity [narrow]) will be summarized by preferred term. Injection site reactions will be summarized by injection site location and number of IP administrations. The summary of TEAEs of hypersensitivity will be presented by PT and will be repeated for events causally related to IP as assessed by the Investigator. Hypersensitivity events will be listed.

Key participant information will be presented for participants with AEs with outcome of death, SAEs, and DAEs. An AE listing for the safety analysis set will cover details for each individual AE.

AEs ongoing at primary DBL will be presented for both primary and final DBL reporting.

AEs will be presented for both, the 16-week placebo-controlled treatment period and the Week 52 end of study reporting.

4.2.8.2 Clinical Laboratory Safety Assessments

All protocol-specified continuous laboratory parameters will be summarized descriptively by absolute value at each visit by treatment group, together with the corresponding changes from baseline. Summary statistics for continuous variables will present n, mean, SD, Minimum, Q1, median, Q3, and Maximum.

All parameters will be summarized in SI units, except for blood eosinophil counts which will be summarized in both SI and conventional units. Results reported by the central laboratory in conventional units will be converted to SI units for reporting.

Central laboratory reference ranges will be used for the identification of abnormalities, and a shift table will be produced for each laboratory parameter to display low, normal, and high values. The shift tables will present baseline and maximum/minimum on-treatment value, as

applicable for each parameter and will include participants with both baseline and post-baseline data.

Shift plots showing each individual participant's laboratory value at baseline and at maximum/minimum post-baseline will be produced for each continuous laboratory variable. If any laboratory variables show any unusual features (high or low values or a general shift in the data points) at other time points, then shift plots of these data may be produced.

Data for participants who have treatment-emergent changes outside central laboratory reference ranges will be presented. This data presentation will include all visits for those participants.

Maximum post-baseline TBL elevations by maximum post-baseline ALT and AST will be presented, expressed as multiples of the ULN. TBL will be presented in multiples of the following ULN: ≤ 1.5 , $>1.5-2$, >2 . AST and ALT will be presented in multiples of the following ULN: ≤ 1 , $>1-3$, $>3-5$, $>5-10$, >10 .

Maximum post-baseline TBL will be presented (<2 and ≥ 2 x ULN) and plotted against maximum post-baseline ALT (<3 , $\geq 3-5$, $\geq 5-10$, and ≥ 10 x ULN), expressed as multiples of ULN. This will be repeated to show maximum post-baseline TBL against maximum post-baseline AST.

For urinalysis data, a shift table will be generated to present changes from baseline to maximum/minimum post-baseline value, displaying normal and abnormal values for selected parameters and will include participants with both baseline and post-baseline data.

Any data outside the central laboratory reference ranges will be explicitly noted on the listings.

Laboratory parameters will be presented for both the 16-week placebo-controlled treatment period and the Week 52 end of study reporting.

